## Common Terms List

Enroller – person who works with potential study participants to complete prescreening and explain study. This will be Investigator [name] or designee.

Participant – one who is willing and able to voluntarily participate in this study.

Aroma Inhaler – A small tube-shaped device about the size of a lipstick container. It contains a pure cotton wick. This wick is impregnated with pure essential oil. This is done at the manufacturer site. An Aethereo®Stick is used for this study. See appendix B for more information.

Aromatherapy – the use of aromas usually in the form of essential oils to impact a person's feelings of health and wellbeing.

Bergamot essential oil – is a citrus essential oil extracted from the rind of the fruit Bergamot (*Citrus bergamia*). The aroma is described as sharp, fruity, powdery, and refreshing. Research shows that chemical constituents found in Bergamot (linalool and linalyl acetate) may impact nerve receptors to bring about anxiolytic effects.

Randomized Controlled Trial (RCT) – a type of study where participants are randomly assigned to either an intervention or a control group. In this way, the risk of bias is decreased. Packets are distributed in an exact order and the Enroller does not pick which participants go into groups.

Random Number Table (RNT) – used to minimize risk of bias in studies. A table of numbers generated in an unpredictable, haphazard sequence.

Master Log Sheet (MLS) – Securely maintained Excel spreadsheet used to track assignment of participants to intervention or control groups. Also used to track those who are ineligible as determined by prescreening survey.

## Research Summary

### Updates to Study Protocol

Update: IRB amendment 09262022 (Appendix G)

To allow Stages one, two, and three and peer recovery persons to participate.

Update: IRB Amendment 08312022 (Appendix H)

To recruit and consent participants online

Update: From QIP Audit 10252022 (Appendix I)

Annual Review with approval received 7/29/2023

8/23/2023 Per email communication with co-I [name], BMed no longer using site approval forms. I have approval to proceed with recruitment when IRB approval is obtained.

Update to consent process 8/2023 (completed)

Communication with participants, begin using RedCap WVU for all surveys and emails. WVU phone and computer for all communication.

10/23/2023 Update: Will no longer include copy of consent in study packets mailed to participants. This will save on mailing costs. Participants can download and print or save to their devices. Approved 11/7/2023

11/21/23 Submitted amendment re: addition of [name] and [name] CITI training certificates to the protocol

12/27/23 Amendment to add a population from Health Right, approved 2/5/2024

## Study Population

Adults (>18 years) who are currently receiving treatment for SUD in the outpatient treatment program at West Virginia University Chestnut Ridge Center (WVUCRC) (n = 340 approx.).

Inclusion criteria are patients diagnosed with SUD who have completed intensive acute phase 1 treatment, and who desire to pursue continuous recovery phases (per facility protocol). All participants must be alert and oriented, provide written consent, and be able to read and write English.

[figure not shown]
Exclusion criteria are patients diagnosed with severe mental illness (who cannot consent to participate), have a medical history of asthma or other serious respiratory disease, and known allergy to citrus. There are no exclusion criteria for gender, race, and/or ethnicity.

Anyone who meets inclusion criteria in the sample population is invited to participate. I am advertising throughout entire population of the study.

## Study Design

The purpose of this study is to see if Bergamot, an aroma therapy essential oil, has any effect on comfort, ease, and stress. Participants will be asked to use a bergamot aroma inhaler, which is a small tube about the size of a lipstick container, at least three times a day for one week. Comfort, ease, and stress will be measured with self-report survey at the beginning and at the end of the week. In addition, participants will be asked to complete a daily logbook to record use of the inhaler. The study lasts for one week (7 days). The aims of this study are to explore the effects of Bergamot essential oil on comfort, ease, and stress in adults in a SUD treatment program, and to evaluate the feasibility of this type of aroma therapy intervention.

## Study Duration (7 days)

## Study Time Involved for Participants

Time involved in completing prescreening, informational session, & pre-surveys

	Step	What is happening	Who does what	Approximately how much time to expect
1	Prescreening	6 question survey	Administered by Enroller	2-3 minutes
2	Open packet & review contents Complete CONSENT	Looking at contents of packets	Enroller reviews consent & participant will either sign or decline	5-10 minutes
2a	Trying out aroma inhaler & giving directions for use	Participant opening their own aroma inhaler	Participant opens aroma inhaler. Enroller demonstrates correct use using their own inhaler	1-2 minutes
2b	Personalizing packet for each participant	Adding dates and organizing packet, going	Enroller adds dates with participant	2-4 minutes

		over logbook together	involvement. Enroller explains follow up texts or emails that participant will begin receiving the next day.	
3	Complete 3 pre-surveys	69 questions (28 GCQ, 20 Ease, 21 DASS)	Participant does this and then they are excused	5-6 minutes
			TOTAL	

More time can be taken to complete these steps and participants may request to meet with the Enroller again if they still have questions.

Time involved in study activities from day 1 to day 7 and completing post-surveys

	Step	What is happening	Who does what & extra details	Approximately how much time to expect
1	Using aroma inhaler 3 x day x 7 days	Participant inhales aroma from inhaler for approximately 1 minute on 3 separate occasions during each day of the study	Participant is responsible. Reminders are sent via text or email during the first 3 days of the study. This reminder should not add any extra time to the study	21 minutes
2 Intervention	Filling out daily logbook x 7 days	Participant puts an X or check mark next to the 3 spaces to document use of aroma inhaler. Also, at the end of the participant's day, Comfort is rated on a 0-10 VAS.	Participant is responsible. A place for comments is available and participants may take their time to add comments about the day (this is discretionary)	7-10 minutes

2 Control	Filling out daily logbook x 7 days	At the end of the participant's day, Comfort is rated on a 0-10 VAS.	Participant is responsible. A place for comments is available and participants may take their time to add comments about the day (this is discretionary)	Same as Intervention group
3	Completing post surveys/ logbook	Participant is completing the logbook for 7 days. Then is opening prepaid postage envelope and completing post surveys	Participant is completing these that include the GCQ, Ease, DASS, and post aromatic survey. They are then sealing the envelop and mailing back to WVU CRC (preaddressed)	5-6
			TOTALS	34-37 minutes

## Background & Significance

### Prevalence Information

During 2017–2019, the annual average prevalence of past-year substance use disorder in West Virginia was 13.4% (or 24,000), similar to both the regional average (15.1%) and the national average (14.7%) (SAMHSA, 2020). The population is ages 18-25. Overdose and opioid related mortality rates, comparing Appalachian and non-Appalachian portions of states, ages 15 to 64 in 2015, 59.7% of diseases of despair were related to overdose of opioids. WV has no non-Appalachian portions of the state (Meit et al., 2017). Nationally, 1.6 million people had an opioid use disorder in the past year ((2019 National Survey on Drug Use and Health, 2020).

.

## Significance to Nursing

This grant proposal is based on holistic nursing research principles (Helming et al., 2022), including work with a marginalized population of those in recovery for substance use disorder (SUD) in north central Appalachia. This study also aligns with National Institutes of Health (NIH) National Center for Complementary and Integrative Health (NCCIH) standards to advance the evidence base for integrative complementary therapies such as aromatherapy through a whole person health approach (NCCIH, 2021). The positive impact of this aromatherapy intervention is to increase comfort and ease, while reducing stress.

## Background

West Virginia is at the epicenter of the opioid addiction crisis with hardly a family left untouched by the devastating consequences (Governor's Council on Substance Abuse Prevention and Treatment, 2020; Saloner et al., 2019). Compared to the rest of the United States, West Virginians are disproportionately affected by deaths due to "diseases of despair", such as drug overdose (Merino et al., 2019; SAMHSA, 2018). Those who make it into recovery programs are often plagued by anxiety and depression (Cicero & Ellis, 2017; Johannessen et al., 2019; Yang et al., 2020) with the most common concurrent mental health issues being depressive disorder, stress, and anxiety (Hutton et al., 2017; Roos et al., 2020). Relapse prevention is key (SAMHSA, 2018). It is recommended that aromatherapy (such as using an aroma stick with bergamot essential oil) has the potential to support those in recovery (Wesa, 2004).

Substance use disorder is characterized by a cluster of physiological, behavioral, and cognitive symptoms occurring when recurrent use of alcohol and/or drugs causes significant impairment, disability, and failure to meet major responsibilities (SAMHSA, 2018; World Health Organization [WHO], 1992). Those in treatment have identified that increasing the level of comfort during substance use recovery is vital (Yang et al., 2020). Integrating aromatherapy could help improve perception of comfort and ease and reduce stress which could support healthy choices and encourage recovery program progression.

Aromatherapy has long been used as a non-pharmacologic treatment alongside medical treatments for various health conditions (Armstrong et al., 2019; Buckle, 2015; Coelho et al., 2017; Herz, 2009; Lizarraga-Valderrama, 2021; Perry & Perry, 2006). Specifically, bergamot (*Citrus bergamia*) essential oil (natural plant based oil) has been reported as one of the most commonly used essential oils because of its effectiveness, low price point, and safety when used via inhalation (Chang & Shen, 2011; Han et al., 2017; Navarra et al., 2015). Bergamot essential oil has the ability to bind to GABAergic receptors and influence the hypothalamic-pituitary-adrenal axis (HPA) providing possible explanation for its anxiolytic properties (Morrone et al., 2007; Saiyudthong & Marsden, 2011). Over the decades, bergamot essential oil has been successfully among persons with mood alterations including anxiety, depression, and stress (Lizarraga-Valderrama, 2021; Mannucci et al., 2017; Perry & Perry, 2006; Scuteri et al., 2017).

## Objectives

Purpose:

The purpose of the study is to examine the effect of an aromatic intervention using bergamot essential oil on comfort, ease, and stress in adults in a SUD recovery program.

Primary Objectives & Aims:

The innovation of this study is to use bergamot essential oil to improve perception of comfort and ease and reduce stress among the marginalized population in a SUD recovery program in rural Appalachia.

Specific Aim #1: Pilot test bergamot essential oil intervention with adults in a substance use disorder recovery program.

**Hypothesis 1a:** Participants in the intervention group will report higher scores on comfort and ease than those in the control group.

**Hypothesis 1b:** Participants in the intervention group will report lower scores in stress than those in the control group.

Specific Aim #2: Evaluate the feasibility and acceptability of an aromatherapy intervention by examining recruitment, enrollment and retention rates, intervention fidelity, and cost analysis.

## Study Design & Methodology

The study uses a parallel-randomized control group comparison design. Data will be collected from participants daily and post intervention.

For Aim #1, descriptive and bivariate analysis will be conducted. Statistical assumptions will be tested. Sample demographics will be reported.

For Aim #2, descriptive statistics will be used as well as participant recruitment, enrollment, and retention rates. Reasons for non-participation and attrition will be recorded. Percentage of intervention consistency will be calculated, and cost of the intervention will be determined.

## Risk

This study is only minimal risk because it involves aroma of a citrus essential oil named Bergamot. This essential oil is impregnated on a pure cotton wick within a manufacturer-sealed aroma inhaler. Participants are instructed and will demonstrate back to the researcher that they will use the inhaler in the prescribed fashion. Participants encounter odors and aromas during daily life and the anticipated magnitude of harm or discomfort anticipated in the

research is not greater in and of itself than those ordinarily encountered in daily life or during the performance of routine physical or psychological examinations or tests.

Potential risks or discomforts include a dislike of the scent or possibly a headache because of inhaling the essential oil aroma from the aroma inhaler. If headache or feeling of dislike continues the participant is asked to discontinue use of the aroma inhaler and contact me, [name], at [[contact]](mailto:[contact]) for further instructions.

This study does include surveys that ask questions about feelings of comfort, ease, and stress. This may cause distress to some participants. Should a participant experience or express any psychological distress or disclose information that indicates a need for urgent psychological or clinical care, the researcher will connect the participant with their provider.

## Benefits

The participant may or may not directly benefit from participating in this research. The knowledge gained from this study may eventually benefit others.

## Statistical Analysis Plan

Data analysis For Aim 1, Descriptive (frequencies, means, ranges, standard deviations) and bivariate analysis will be conducted on the demographics, GCQ, Ease measure, and DASS scales. Statistical assumptions (i.e., normal distribution and homogeneity of variances etc.) will be tested. Sample demographics of patients will be reported. Fisher's exact test will be used for categorical variables; Repeated measures ANOVA and paired t-test will be used for continuous variables. Pearson's and Spearman's correlation analyses will be used to explore relationships among variables (Pallant, 2020). The statistical significance is set at a 5% (alpha = 5%). All analyses will be completed using Statistical Package for the Social Sciences (IBM SPSS).

For Aim 2, Descriptive statistics will be used to analyze Aim 2a. Participant recruitment, enrollment, and retention rates will be tabulated and reported. Reasons for non-participation and attrition will be recorded and will be used to develop strategies to address this. For Aim 2b, adherence to the intervention protocol will be calculated from responses in the logbooks. For Aim 2c, to determine the cost of the intervention implementation, all charges related to implementation are calculated. This includes costs of personnel time for administering each session, the materials, and incentives.

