## Sample Size

Sample size was calculated using G\*Power v.3.1.9.7 on repeated measure ANOVA given  $\alpha=0.05$ , moderate effect size (0.25), power of 80%, two groups with 2 measurements, correlation among repeated measures (0.50), a total sample size of 98 will be required. A total sample size of n=49 for intervention group and n=49 for control group is sought.

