## Prior to opening a Study Packet

1. In a private location, Enroller will determine eligibility for this study.
  - a. Inclusion criteria are as follows:
    - i. Older than 18 years of age
    - ii. Currently enrolled in treatment
    - iii. Have completed intensive phase 1 and wish to continue with treatment
    - iv. Alert & oriented
    - v. Able to provide written consent
    - vi. Able to read & write English
  - b. Exclusion criteria are as follows:
    - i. Diagnosed with severe mental illness
    - ii. Medical history of asthma
    - iii. Other serious respiratory disease
    - iv. Known allergy to citrus
2. In a private location, Enroller will prescreen using created survey tool (appendix A)
  - a. Use the prescreening survey provided
  - b. Read prescreening survey to participants and record answers
  - c. If not contraindicated by prescreening questions, allow participant to smell the aroma inhaler (3 inches from nose)
    - i. Record all reactions, “liked the smell”, “sneezed”, “said ‘yuck’” on the presurvey. Record “no negative reactions” as applicable (This is a vital component of aromatic research)
3. IF PARTICIPANT IS INELIGIBLE, thank them for their time, note on MLS that they were screened and why they were ineligible. Use the special section at the end of the MLS to make this notation. Do not use an Id # space. Write “ineligible” and the date across the top of the survey.
4. IF PARTICIPANT IS ELIGIBLE, file prescreening form in predetermined place and obtain a study packet in the order they are arranged (001-098)
  - a. Enter date and name of participant on the **Random Number Table (RNT)** sheet
5. Record Unique Identifier packet number on **Master Log Sheet (MLS)**
  - a. Use MLS to track Participants
  - b. This Unique Identifier number is already on every document in each packet

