- c. On day 1, 2, & 3 a text or email messages will be provided to participants to remind them to complete their diary indicating if they used the inhaler and mark how they are feeling on the VAS. They will be instructed to contact the researcher with any questions.
- d. Days 4, 5, 6, & 7, participants will not receive reminders.
  - i. A reminder will be sent on day 7.
  - ii. After day 7, all participants will open their final survey packet included in the folder.
  - iii. They will be instructed to complete the survey packet and return it and the logbook using the prepaid postage envelope.

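### The plan does not say which ANOVA term decides the between-arm hypotheses; its N of 98 fits the group main effect, not group×time, and adjusting for the pre score would be a better test at no cost

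*Combined protocol and SAP*

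**What the plan says.** Both hypotheses under Objectives are comparisons between arms. Hypothesis 1a reads "Participants in the intervention group will report higher scores on comfort and ease than those in the control group", and Hypothesis 1b reads "Participants in the intervention group will report lower scores in stress than those in the control group". Each outcome has a pre and a post score: "Comfort, ease, and stress will be measured with self-report survey at the beginning and at the end of the week".

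For continuous outcomes, the Statistical Analysis Plan states "Repeated measures ANOVA and paired t-test will be used for continuous variables". It gives neither method a role and names no ANOVA term (group, time or group×time). Study Design & Methodology adds only that descriptive and bivariate analyses will be done for Aim 1. Adjustment for the pre score is not mentioned in the supplied text.

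The Sample Size section also relies on repeated measures ANOVA. It takes alpha 0.05, an effect size of 0.25 and 80% power, and continues: "two groups with 2 measurements, correlation among repeated measures (0.50), a total sample size of 98 will be required". It splits this into 49 per arm. No term is named here either.

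**The concern.** Of the listed methods, only some can answer the question asked. A paired t-test shows whether an arm changed over the week, not whether the arms differ. Within a two-group, two-time repeated measures ANOVA, the time term has the same limitation. The group term does compare arms, but on the average of pre and post scores. The pre surveys are completed when the packet is opened, before the seven days of use begin, so that average halves any effect that appears only at post. Group×time compares change between arms and is the natural ANOVA test of both hypotheses.

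Two things are at stake. First, with no deciding term named, the choice between the group and group×time terms, or a reading based on within-arm p-values, can be made after the results are known. Second, the stated 80% power may belong to a test that will not be used. There is also an efficiency question: the pre score is already collected, and using it as a covariate estimates the arm difference more precisely than comparing changes.

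**Working it through.** **Inputs from the plan.** f = 0.25, alpha 0.05, power 80%, two groups, m = 2 measurements, correlation r = 0.50, N = 98 (n = 49 per arm). Sidedness is not stated; two-sided tests are used here.

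**Step 1: reproduce N = 98.** Noncentral F with 1 and N − 2 degrees of freedom, as in G\*Power's repeated measures options:

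- Group main effect: λ = N·f²·m / (1 + (m − 1)r). At N = 98, λ = 98 × 0.0625 × 2 / 1.5 = 8.17 and power is 0.808. At N = 96 power is 0.799. With equal arms the answer is 98, as stated.
- Group×time: λ = N·f²·m / (1 − r). At N = 34, λ = 34 × 0.0625 × 2 / 0.5 = 8.5 and power is 0.807 (0.781 at N = 32). At N = 98, λ = 24.5 and power is 0.998.

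Of these two between-arm terms, only the group term gives 98.

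**Step 2: what f = 0.25 means at the post survey.** Suppose the arms are equal at pre and differ by d SD at post.

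- Group term: the averaged difference is d/2, each arm lies d/4 from the mean, so f = d/4.
- Group×time: the interaction effects in the four cells are ±d/4, so again f = d/4.

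Under either term, f = 0.25 means d = 1.0 SD.

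**Step 3: power of the candidate tests for a post-only effect d.** Noncentral t, SD = 1, n per arm:

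- Group term: difference d/2, SE = √[(2/n)(1 + r)/2]
- Group×time (the same as a t-test on change): difference d, SE = √[(2/n)·2(1 − r)]
- ANCOVA on pre score: difference d, SE = √[(2/n)(1 − r²)]

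With n = 49, r = 0.5 and d = 0.5, the ratios of difference to SE are 0.25/0.175 = 1.43, 0.5/0.202 = 2.47 and 0.5/0.175 = 2.86.

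| Scenario (two-sided 5%) | Group term | Group×time | ANCOVA |
|---|---|---|---|
| d = 1.0, r = 0.5, n = 49 | 80.8% | 99.8% | >99.9% |
| d = 0.5 (assumed), r = 0.3, n = 49 | 33% | 54% | 73% |
| d = 0.5 (assumed), r = 0.5, n = 49 | 29% | 69% | 81% |
| d = 0.5 (assumed), r = 0.7, n = 49 | 26% | 89% | 93% |
| d = 0.5, r = 0.5, n = 44 (assumed 10% loss) | 27% | 64% | 76% |
| d = 0.5, r = 0.5, n = 39 (assumed 20% loss) | 24% | 59% | 71% |

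ANCOVA's gain over group×time at 0.5 SD is 18, 12 and 4 percentage points at r = 0.3, 0.5 and 0.7. A simulation of 40,000 trials at d = 0.5, r = 0.5 and n = 49 gave 30%, 69% and 81% for the three tests.

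**Step 4: completers needed in total for 80% power at d = 0.5.** At r = 0.3, 0.5 and 0.7: ANCOVA 118, 98 and 68; group×time 178, 128 and 78. ANCOVA returns the plan's 98 at r = 0.5 only because (1 + r)/2 and 1 − r² both equal 0.75 there.

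**The case against.** The strongest reply is that the plan does name a method. Repeated measures ANOVA appears in both the analysis and the sample size sections, and with two groups and two times most readers would take group×time as the test. That term is valid, and naming it would close the gap. This stands: what is missing is the deciding term, and ANCOVA is an improvement in precision, not the repair of an invalid test.

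It is also fair that 81% against 69% does not come from the plan's inputs. A reader might infer that the trial was sized for a 0.5 SD post-score difference and is underpowered for group×time. The documents do not support that. With arms equal at pre, the plan's f of 0.25 means 1.0 SD at post under either term, and group×time then has 99.8% power. The 0.5 SD case shows only what happens if the effect is half as large. The gain also shrinks as r rises, and the plan gives no source for r = 0.5.

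A reader might further infer that paired t-tests are meant to decide the hypotheses. Nothing says so; a within-arm follow-up is an equally natural reading.

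Lastly, Aim 1 is described as pilot testing. That lowers the stakes, but the plan states directional hypotheses, a 5% significance level and 80% power, so it should still say which test these refer to.

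On loss of post surveys, packets are numbered to 98 ("obtain a study packet in the order they are arranged (001-098") and no allowance is stated. The procedures have post surveys returned by post ("They will be instructed to complete the survey packet and return it and the logbook using the prepaid postage envelope"), but the August 2023 entry under Updates to Study Protocol moves all surveys to REDCap. Postal return is therefore not safe evidence of how many will be lost, and the 10–20% above is purely illustrative.

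**Conclusion.** The point holds in a limited form. The term that decides Hypotheses 1a and 1b is not named, one of the two listed methods cannot test them, and the 80% power at N = 98 belongs to the group main effect, which dilutes a post-only effect by half. The plan nowhere says that this term will decide.

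How much this matters depends on the true effect. At 1.0 SD, group×time and ANCOVA both have ample power and the choice between them hardly matters. At an assumed 0.5 SD, the choice of term moves power from 29% (group) to 69% (group×time), and using the pre score as a covariate raises it to 81%. These figures rest on equal arms at pre, equal SDs at both times, r = 0.5, 49 completers per arm and two-sided 5% tests. One-sided testing at 5% would give 88% for ANCOVA and 79% for group×time, leaving the order unchanged. This should be fixed, but it does not undermine the randomised design or the data being collected.

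**What to change.** Before outcome data are examined, amend the Statistical Analysis Plan to state that comfort, ease and stress are each decided by an ANCOVA of the post score on arm, adjusted for the pre score, and reported as an adjusted mean difference with a 95% confidence interval. Within-arm changes should be descriptive only.

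Restate the Sample Size section for that test: 98 completers give about 81% power for a 0.5 SD post-score difference at r = 0.5 (73% at r = 0.3, 93% at r = 0.7). Say that the figure refers to completers and that power is lower if post surveys are lost, about 76% to 71% at an assumed 10–20% loss.

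If repeated measures ANOVA is kept, name group×time as the deciding term and restate the power for it: 99.8% for 1.0 SD and 69% for 0.5 SD, both at r = 0.5 with 98 completers.

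Either route costs only a few sentences. The pre scores are already collected, SPSS runs both analyses, and no new measurement is needed.
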